#### **Previous Protocols**

Version	Version Date	Approval Date
1.0	09/17/2018	10/02/2018
1.1	10/24/2018	11/15/2018
1.2	06/24/2019	08/14/2019
1.3	09/12/2019	10/30/2019
1.4	11/15/2019	12/13/2019
1.5	01/01/2020	01/13/2020
1.6	03/25/2020	06/01/2020
1.7	09/30/2020	10/05/2020
1.8	02/18/2021	02/25/2021
1.9	11/03/2021	11/30/2021
2.0	10/17/2022	02/15/2023

## *STAT-PD: Preventing Levodopa Induced Dyskinesia in Parkinson's disease with HMG-CoA Reductase Inhibitors*

### Background and Significance

**Parkinson's Disease (PD) and Levodopa Induced Dyskinesia (LID):** The enthusiasm that accompanied the invention of levodopa for the treatment of the disabling symptoms of Parkinson disease in the late 1960s, was tempered by realization that abnormal movements resembling chorea (but other hyperkinetic movements too) would eventually develop in most chronically treated patients. The term "levodopa induced dyskinesia" (LID) was eventually coined; and scientific inquiry into one of the most puzzling and difficult to treat complications of therapy for PD has eluded a satisfactory solution.

It is reported that up to 50-80% will develop LID within 5 years of L-dopa treatment[1], 80-90% by 10+ years of treatment[2]. There is variability within patients making it difficult to predict when a patient will develop LID; probable risk factors include earlier age at onset of PD, longer duration of L-dopa treatment, initial levodopa dosage, cumulative levodopa dose exposure, female gender, years of disease duration, disease severity and possibly genetic factors[3,4,5,6,7,8]. Cerebrovascular disease was not associated with motor complications, but was associated with pneumonia in another study(9). [3]. In the beginning, LID expression is mild (often unnoticed by the patient) and becomes higher amplitude over the years, or in other words, it becomes more severe.

Quality of life surveys suggest that mild LID is not disabling, but as LID becomes more severe, LID can deteriorate quality of life [4][5]. In a large European 60 center study of the effect of LID on QoL, LID was shown to be associated with depression and significant reductions on all four components of the Parkinson Disease Questionnaire (PDQ-39), a validated survey of quality of life in PD. For example, the "social functioning" subscore was almost 50% worse in those with the highest LID levels compared to those with the mildest severity [12]. The odds were 2.8-3 times higher of being depressed or anxious if the patient also experienced LID in a study of >400 Chinese PD patients [13]. In another European multicenter study LIDs had detrimental effects on the PDQ-39 dimensions of activities of daily living, cognition, stigma, and bodily discomfort [14]. A recent study determined that increasing scores on the London Handicap Score were determined by LID as well as OFF motor scores [15]. Another insight into the effect of LID on QoL comes from a study of early PD patients. Here, the authors determined that in the early years when LID is mild, it does not affect QoL [16]. This is not surprising, as LID is typically mild/ unobtrusive in the early years, but will worsen in amplitude over time. Likely, more severe LID becomes a determinant of QoL. Veterans with PD scored lower in physical and mental health related quality of life scores than those with angina/coronary heart disease, arthritis, chronic low back pain, congestive heart failure, diabetes, and stroke [19].

Dyskinesias also increase cost of care substantially[6]. As 2% of Veterans are diagnosed with PD, and over 55,000 receive care in the VA system[7], it follows that the problem of dyskinesia is clinically significant and costly, not only in financial terms, but in diminished quality of life. Indeed, Veterans with PD and its attendant problems scored lower in physical and mental health related quality of life scores than those with angina/coronary heart disease, arthritis, chronic low back pain, congestive heart failure, diabetes, and stroke[8].

**Current treatments:** The only preventive strategies are to delay use of dopaminergic medications, particularly levodopa. Many patients or their treating clinicians fear LID so much that he/she will avoid taking levodopa until they become quite parkinsonian[9]. Once LID is established, the only medication accepted for use (though no drug is approved) to diminish its severity is amantadine[10], or else reduce

dopaminergic medication use, which can again cause worsened parkinsonism. The last alternative is invasive deep brain stimulation surgery; which is costly and not without risk

**Underlying Mechanisms of the development of LID:** The mechanisms underlying the development and expression of LID are complex; our understanding of the cascading pathway of post-receptor molecular mechanisms triggered by dopamine receptor -1 (D1) pathway stimulation (striatum D1 receptors are occupied by dopamine generated by levodopa administration) in abnormal basal ganglia is still incomplete. However, these new insights have produced new targets for preventive interventions in ways not previously imagined.

Dopamine receptors are metabotropic G-coupled protein receptors classified as D1-like (D1 and D5 subtypes) or D2 like (D2-4 subtypes). LID is closely associated with sensitization of D1 receptors which are linked to the “direct” pathway, a circuit that links the striatum with the output nuclei the globus pallidus interna (GPI) and substantia nigra pars reticulata.

Dopamine cell denervation of the substantia nigra coupled with pharmacologic replacement dopaminergic priming cause functional/anatomical changes in the striatum. It is generally agreed that LID results from pulsatile stimulation of striatal postsynaptic dopamine receptors (by short-acting levodopa) with subsequent associated downstream changes in gene/protein expression, particularly in the medium spiny neurons (MSN) of the striatum[11].

Sensitized striatal MSNs become persistently hyper-responsive. This is likely the result of the dopamine-depleted state and resultant over-expression of parts of the D1 receptor signaling/transduction pathways coupled with persistent exposure to levodopa; sensitization the result of increased stimulation of adenyl cyclase. This coupling then causes activation of various protein kinases. Stimulation of protein kinase A (PKA) causes phosphorylation of dopamine- and cAMP-regulated phosphoprotein (DARPP-32) which inhibits protein phosphate (PP1). In turn, that suppresses dephosphorylation of several targets of PKA, all part of the cascade towards LID in causing changes in the excitability of striatal MSNs. Loss of long-term potentiation and inadequate beneficial depotentiation seems important to the genesis of LID due to the loss of the striatum’s ability to eliminate extraneous information and normalize synaptic efficiency.

Changes in synaptic plasticity result from alterations in signaling pathways involved in gene regulation and enzyme expression. Extracellular regulated kinases 1 and 2 (ERK1/2), are serine/threonine kinases that are members of the mitogen-activated protein kinase signaling pathway, and are major regulators of transcription/translation as well as long term potentiation within the striatum[12].

[figure not shown]
Hyperphosphorylation and therefore increased activation of ERK1/2 via PKA/DARPP-32 has consistently been associated with LID and expression of several immediate early genes like Nur77, ΔFosB, Zif268 and activity-related cytoskeletal associated protein. This abnormal upregulation ultimately prevents the healthy depotentiation of the striatum perhaps by causing phosphorylation in subunits of the AMPA glutamate receptor (GluA1 subunit)[13]. It has even been proposed that ERK1/2 upregulation may link to the angiogenesis or microvascular remodeling seen in the brains of PD patients and in rats with LID. Inhibition of ERK 1/2 will inhibit this remodeling in the rat model[14]. Other molecular alterations have been described such as increases in protein MSK-1, histone H3 and CREB phosphorylation as well as activation of mammalian target of rapamycin complex 1 (mTORC1), changes which correlate behaviorally in animals with LID expression[15][16].

**Pre-clinical evidence for statins to prevent LID development:** Given that activation of the Ras-extracellular signal regulated kinase 1/2 (ERK 1/2) is likely associated with development of LID, it follows that blockade of ERK phosphorylation may reduce the expression of LID[17]. Specifically, statins inhibit Ras isoprenylation, therefore can subsequently impede phosphorylation of ERK 1/2 (pERK 1/2)[18].

In a rat model of Parkinsonism and dyskinesia, animals that were pretreated with simvastatin BEFORE levodopa was initiated, compared with vehicle developed 1) less abnormal involuntary movements (AIMS)--which is the animal analogue of dyskinesia, 2) decrease in striatal pERK1/2 3) reduced ΔFosB levels[19].

In another rodent study using lovastatin, the severity of abnormal involuntary movements was clearly attenuated (overall by more than 50%) when the drug was applied BEFORE the initiation of levodopa compared to placebo (see Figure A)[20].

*Figure A. Levodopa plus Lovastatin treated animals (L-D + B + L) express significantly less abnormal movements than Levodopa only (L-D + B) treated rodents.*

In the MPTP parkinsonian monkey model, simvastatin reduced the severity of established dyskinesia by 45%. Measurement of pERK1/2 in peripheral B and T lymphocytes (CD3/CD20) in these monkeys was significantly different between the vehicle and simvastatin treated animals[21]. These authors also performed an additional intervention with simvastatin in humans with dyskinesia, however the potential problem with the design of this study was that simvastatin was started long after dyskinesia was established and was used short term, so the opportunity to intervene and reduce the priming process had passed.

*Table 1. Statin and no Statin patients in PD*

**Evidence for statin use affecting development of dyskinesia.** In a retrospective cohort study by Lieberman et al, PD patients with >7 years of disease had no difference in the composite endpoint of dementia, dyskinesia and wearing off, compared to patients who did not take a statin. However, when examined more closely, dyskinesia appears to be less common on the statin treated group[33]. See Table 1 at right.

	No Statin	Statin
Patients	200	45
Male/female	123/72 (1.7) a	36/9 (4.0)
Age (yrs)	70.6 (11.8) b	72.0 (9.4)
Stage (H & Y) c	2.6 (1.2)	2.5 (1.2)
PD duration (yrs)	7-22	7-22
Dementia	17 (8.5%) d	5 (11.0%)
Dyskinesia	43 (22.0%)	4 (9.0%)
Wearing off	90 (45.0%)	15 (33.0%)

5% Patients on agonist only, 45% patients on sinemet only, 50% patients on sinemet + agonist.

a Male/female ratio.

[figure not shown]
b  $\pm$  Standard deviation.

c Stage (Hoehn & Yahr) assessed in 'on'.

d Prevalence of dementia, dyskinesia, wearing off.

[figure not shown]
**Pre-clinical evidence for ERK1/2 levels as a potential dyskinesia biomarker.** In the primary prevention model in which lovastatin was given to the parkinsonian rat before levodopa was commenced, pERK levels in the striatum clearly rose when levodopa alone was administered. This rise was nearly ameliorated with lovastatin. This low pERK correlated with low AIMS (Figure B)

*Figure B. West blot demonstrates low pERK in lovastatin (L-D + B + L) treated rodents compared to levodopa only (L-D + B)*

In an exploratory trial, Tison and others[22] measured ERK1/2 phosphorylation in both monkeys and PD patients. They collected CD3 and CD20 immunoreactive cells (T and B lymphocytes) after whole blood samples were prepared and incubated with an antibody against phosphorylated forms of Tyr 202 and Tyr 204 of ERK 1/2 using a Becton Dickinson kit. In this study described above, monkeys treated with 3 mg/kg of simvastatin co-administered with LD showed a significant reduction in basal pERK levels (>50% reduction, Figure C). In humans, there was a trend towards reduction in pERK levels that did not reach significance.

*Figure C. pERK levels are reduced by 3mg/kg of simvastatin in monkeys.*

**Summary of Background:** Although the biochemical cascading changes that occur in the development of LID are complex, nigral cell loss and chronic LD administration is thought to cause changes in the gene and protein expressions, notably ΔFosB and ERK1/2 amongst many other markers. ERK1/2

hyperphosphorylation in the striatum is implicated in the development of LID as a potential biological molecular marker. Inhibition of ERK1/2 by statins is a putative therapeutic intervention to prevent the biologic cascade leading to dyskinesia. Statin use in rodents and non-human primates with experimental Parkinsonism indicate delay in onset of dyskinesia as well as reduction in the progression of severity over time in LID. While epidemiologic studies of statins and dyskinesia are lacking, data in one study suggested a reduced prevalence of LID in statin-users after 7 years. These studies may also suggest that statin use is optimal when used BEFORE levodopa is begun (priming prevention) rather than secondary prevention, though this remains to be studied further, and there still may be residual benefit to secondary prevention. We can study whether statins can prevent striatum disordered depotentiation and dyskinesia in humans comparing subjects who were prescribed statins for dyslipidemia prior to initiating levodopa (primary prevention) and comparing them to subjects who were not. We can also compare these two cohorts to those who were prescribed statins AFTER starting levodopa to see if there was still a benefit, even if muted (secondary protection). We can test whether pERK levels correlate with each cohort's statin exposure level, as we might expect the lowest levels in those with the longest statin exposure and therefore the least LID.

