#### ***Inclusion and Exclusion:***

##### **Inclusion Criteria:**

- PD subjects will be evaluated using the UK Brain Bank Criteria (UKPDBB) [31]. The UKPDBB is a widely accepted clinical criteria for the diagnosis of pd. This is an autopsy-correlated set of criteria that differentiates between Parkinsonian-related disorders, Parkinsonism, and true PD. The clinical diagnosis using the UKPDBB has shown good sensitivity (91%), and specificity (98%), and good positive predictive value (99%) when examined with pathological criteria of PD.
- Age diagnosed  $\geq$  50 years.
- Treatment with levodopa a minimum of 5 years ( $\geq$  5, to allow LID time to develop)
- Statins for cohort A for duration of levodopa treatment
- Statins may be discontinuous for duration of levodopa treatment in Cohort B

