Additionally, pERK1/2 levels will be examined. Initial analysis will examine the relationship between severity of dyskinesia (with the AUC of the RMSV) and pERK1/2 levels using correlations. Further analysis will examine if pERK1/2 levels vary by cohort using ANOVAs and multiple regression techniques. Assessment of confounders of the relationship between pERK1/2 and dyskinesia severity will be examined.

**Sample Size:** Based on results of a validation study of dyskinesia scales [35], using a one-way ANOVA to examine the difference in part 3, impairment, of the Unified Dyskinesia Rating Scale (UDysRS) between the three pairwise comparisons, 37 participants are needed in each group to detect a moderate effect size ( $f=0.30$ , at least one group difference of 3.75 points) with a significance of 0.05 and power of 0.80. Pairwise comparison of statin before levodopa versus no statin will receive priority. To account for drop outs, an additional 3 participants will be included in each of the groups. Additional 10 will be included for screen failures (total 130). Total enrollment will be 40 per group, 120 total. See Table 5 for estimated recruitment goals.

*Table 5. Estimated Recruitment Totals per Site*

	VAPORHCS	VAPUGHCS	OHSU	Total
Recruitment	60	28	32	120

*Figure 1. Recruitment Goals over time*

Subjects were described previously and in the first cohort will be those who had been on a statin first and remained on it while they were initiated on LD. The second cohort will be those who started a statin AFTER beginning LD. The third cohort will be subjects with no history of statin intake. Matching will occur based on gender, severity of disease based on a PD rating scale, and LD dose

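### The pERK1/2 cohort comparison ignores whether participants are on a statin at the blood draw, so a Cohort B result cannot be read as a timing effect

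*Combined protocol and SAP*

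**What the plan says.** **Evidence cited.** Background and Significance reports that "monkeys treated with 3 mg/kg of simvastatin co-administered with LD showed a significant reduction in basal pERK levels". Of patients it says: "In humans, there was a trend towards reduction in pERK levels that did not reach significance". The stated expectation is framed as length of exposure: "as we might expect the lowest levels in those with the longest statin exposure".

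**Exposure groups.** Inclusion Criteria has "Statins for cohort A for duration of levodopa treatment" and "Statins may be discontinuous for duration of levodopa treatment in Cohort B". The paragraph after Sample Size defines B only by a statin start after levodopa and C by no statin history. It describes Cohort A more loosely, as those "on a statin first and remained on it while they were initiated on LD".

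**Analysis.** Data Analysis first correlates pERK1/2 with the force-plate dyskinesia AUC. It then says: "Further analysis will examine if pERK1/2 levels vary by cohort using ANOVAs and multiple regression techniques". The same section also lists pERK1/2 among the secondary outcomes compared between groups by the adjusted regression. The named covariates do not include current statin use, although the list is left open.

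**Data available.** The Screening and Day patient Visits sections collect past statin use and current medications. Medicines that are not for Parkinson's disease are continued on the test day.

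**The concern.** A level measured on one day in treated lymphocytes would plausibly depend on whether the drug is being taken then. The cohort labels record something else: the order in which statin and levodopa were started. For A and C the two agree, at least under the inclusion criterion. For B they need not, because B can hold both current and former users.

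The plan's hypothesis places B between A and C. A B cohort in which some people have stopped also falls between A and C if pERK1/2 follows current use alone. The cohort analysis gives the same picture in either case, and more participants would not separate them. At stake is a misreading: a null or intermediate B could be reported as evidence that a late start inhibits ERK less, when it may only show that some of B were off the drug.

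**Working it through.** **1. The plan's own figure.** Sample Size gives 37 per group for a one-way ANOVA with f = 0.30, alpha 0.05 and power 0.80. The noncentrality is N × f² = 111 × 0.09 = 9.99, and the noncentral F power is 0.803 (36 per group gives 0.792). The figure reproduces. It was set for UDysRS part 3, so the plan states no power for pERK1/2.

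**2. Assumptions.** The documents give neither a human pERK1/2 effect size nor the share of B on a statin. I assume unit SD, an effect d in current users only, full return to the never-user level after stopping, and a share c of B current (all of A, none of C).

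**3. B-C contrast.** The expected difference is c × d. Mixing raises the variance in B to 1 + c(1−c)d², so the pooled SD is √[(2 + c(1−c)d²)/2]. The noncentrality is c × d / (pooled SD × √(2/37)), with √(2/37) = 0.2325. For d = 0.5, two-sided 0.05:

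| Share of B current | Difference (SD) | Pooled SD | Noncentrality | Power |
|---|---|---|---|---|
| 100% | 0.500 | 1.000 | 2.15 | 0.56 |
| 75% | 0.375 | 1.012 | 1.59 | 0.35 |
| 50% | 0.250 | 1.016 | 1.06 | 0.18 |
| 25% | 0.125 | 1.012 | 0.53 | 0.08 |

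Simulation agrees to within about 0.01.

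**4. Larger effects.** With three groups, f = 0.30 corresponds to a largest pairwise difference of 0.30 × 3/√2 = 0.64 SD (two groups equal) or 0.30 × √6 = 0.73 SD (one group midway). Borrowing these, and adding 1.0 SD, B-C power at d = 0.64 / 0.73 / 1.0 is:
- all of B current: 77% / 88% / 99%
- a quarter off statins: 51% / 63% / 86%
- half off: 26% / 33% / 52%
- three quarters off: 10% / 12% / 17%

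**5. Contrasts without B.** A-C does not depend on c. Its power is 0.56 at d = 0.5 and 77% / 88% / 99% at the three larger effects.

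**6. Omnibus test.** At d = 0.5 with half of B current, the means are 0.5, 0.25 and 0, so f² = 0.125/3 = 0.0417. The average within-group variance is 1 + 0.0625/3 = 1.021. The noncentrality is 111 × 0.0417/1.021 = 4.53 and power is 0.45, against 0.58 with all of B current.

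**7. Alternative analyses at d = 0.5, half of B current.**
- Current users against non-users, 56 v 55: noncentrality 0.5/√(1/56 + 1/55) = 2.63, power 0.74. With all of B current (74 v 37) it is 0.69.
- Current use plus a three-level cohort term: A is all current and C all non-current, so the current-use coefficient is estimated only inside B, about 18 v 19. The noncentrality is 0.5/√(1/18 + 1/19) = 1.52 and power about 0.33.
- A against current-user B, 37 v 18, for a timing difference of 0.5 SD: noncentrality 0.5/√(1/37 + 1/18) = 1.74, power 0.40.

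**The case against.** Several objections carry weight.

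- **The main pERK1/2 question does not use cohort labels.** Aim 3, the tertiary endpoint and the initial analysis all concern the correlation with dyskinesia severity. The cohort comparison is a further analysis. This stands and limits the reach of the point.
- **The priority contrast is A-C**, which is not diluted under the inclusion criterion. This also stands. A reader might infer that the whole biomarker comparison is diluted; the documents support that only for contrasts involving B.
- **A reader might infer that B-C is nearly uninformative.** That needs most of B to be off statins and pERK1/2 to return fully to the never-user level. The plan only permits interruption; it gives no share and does not discuss washout. With a quarter of B off statins, B-C keeps 51% to 86% power at 0.64 to 1.0 SD.
- **The gain from a current-use test is easily overstated.** The calculation assumes that only current use matters, and part of the step from 0.45 to 0.74 comes from replacing a 2-df test with a 1-df test: the latter reaches 0.69 with no dilution at all. Adding current use to the cohort model would not give the gain, because power falls to about 0.33.
- **The hypothesis is about length of exposure, and the covariate list is open.** Both are true, so the cohort analysis should stay. But an open list prespecifies nothing, and length of exposure does not separate current from past use.

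None of this answers the interpretive problem. Whenever some of B are off statins, the cohort means alone cannot tell a timing effect from non-use at the draw.

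**Conclusion.** The point holds for the pERK1/2 cohort comparison where it involves Cohort B. The grouping reflects start time, the cited lymphocyte effect is on-treatment, and neither eligibility nor the named covariates deal with statin use at the draw. The size cannot be fixed from the documents. Under the 0.5 SD assumptions, B-C power runs from 0.56 with no interruption to 0.08 with three quarters of B off statins, and omnibus power falls only from 0.58 to 0.45 at half. These figures rest on an effect confined to current users and full return after stopping; partial return would mean less dilution.

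The pERK-dyskinesia correlation is unaffected. So is A-C, provided the inclusion criterion for Cohort A governs. The looser description after Sample Size does not state use up to the draw, and if it governed, A-C could be diluted too. This is a worthwhile, cheap correction to a further analysis and does not undermine the trial's main comparison.

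**What to change.** In Data Analysis, keep the pERK1/2 cohort analysis and prespecify beside it:

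1. A 1-df comparison of pERK1/2 in current statin users (A plus current users in B) with non-users (former users in B plus C), adjusted for the covariates already listed but without a three-level cohort term.
2. A separate timing comparison of A with current users in B, labelled as low-powered.

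Take statin status from the medication list already collected. Confirm it on the day of the draw, since screening may precede that visit by up to 3 months. Report how many of B are current users, and state that B-C will not be interpreted as a timing effect without these results. Reconcile the two descriptions of Cohort A.

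The cost is SAP wording, one confirmed yes/no item and one more exploratory comparison. No visit, sample or participant is added. The drawback is small numbers for A against current-user B.
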